9.1.3 Study Visits 2-6

Study Visits 2-6 are post-randomization weekly assessments during the treatment period. During this period, all adverse events must be recorded, including those associated with treatment, study procedures, or concomitant medication. All weekly visits must be performed according to the study visit schedule (Table 17-1), preferably on the same day each week. Subjects found to have wound closure at a weekly assessment should **NOT** complete that visit but instead go directly to Study Visit 7 (Exit Visit), be discontinued from treatment and have exit procedures performed. A closed ulcer is defined as having complete re-epithelialization, without drainage or the need for a dressing. All study procedures should occur in the order outlined in the protocol. Visits occurring outside the visit window should be completed and recorded as a protocol deviation.

- If the ulcer is closed at this assessment visit, do not complete these procedures. Instead go directly to Study Visit 7 (Exit Visit).
- 2. Record any changes in general health and the use of concomitant medications.
- If any adverse events are observed or reported, they must be recorded as instructed in Section 12, Adverse Events.
- Record the number of dressing changes since the previous study visit and the amount of time spent daily dressing the ulcer.
- Irrigate the wound with normal saline delivered at 4-15 psi using the Irrimax[®] device.
 (Sharp debridement is NOT allowed.)
- Photograph the target ulcer using the ImageIQ EDCIQ mobile imaging system. The target ulcer area (cm²) and percentage of the target ulcer surface covered with necrotic,

- nonviable tissue will be determined by two independent reviewers using the ImageIQ EDCIQ mobile imaging system.
- Ensure that all caregivers are instructed as to the treatment requirements for the study
 protocol and that they are instructed in the application of test article and dressing changes.
 Ensure adequate supplies (test article and dressings) are dispensed.
- Apply the test article to the entire wound bed according to the instructions for use located in the Study Guide, cover with a semi-occlusive dressing (e.g. COVRSITETM). If the wound has depth, saline moistened gauze may be used to fill at the Investigator's discretion.
- 9. Record the time spent dressing the ulcer at this visit.
- Schedule the next weekly assessment in 7 (±1) days.

9.1.4 Exit Visit - Study Visit 7

This is the final visit for all subjects in the study.

- 1. Record any changes in general health and the use of concomitant medications.
- If any adverse events are observed or reported, they must be recorded as instructed in Section 12, Adverse Events.
- Record the number of dressing changes since the previous study visit and the amount of time spent daily dressing the ulcer.

Only if the ulcer remains open at this visit:

Irrigate the wound with normal saline delivered at 4-15 psi using the Irrimax[®] device.
 (Sharp debridement is NOT allowed.)

All subjects:

- 5. Photograph the target ulcer using the ImageIQ EDCIQ mobile imaging system. The target ulcer area (cm²) and percentage of the target ulcer surface covered with necrotic, nonviable tissue will be determined by two independent reviewers using the ImageIQ EDCIQ mobile imaging system. Closed ulcers will be photographed and designated as "closed".
- 6. Assess the wound status using both the PUSH and WBS tools.
- 7. Record the time spent assessing the ulcer.
- All females of child-bearing potential must undergo a urine pregnancy test upon completion or discontinuation from the study.
- 9. Return all used and unused study medication to a secure area for accountability
- Dismiss the subject from the study. Institute appropriate standard ulcer care for ulcers remaining open at the discretion of the Investigator.

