8.1 STUDY DESIGN

This is a randomized, controlled, parallel observer-blind group study. Subjects providing informed consent will be screened against the inclusion/exclusion criteria. Subjects who meet all of the inclusion criteria and none of the exclusion criteria will be randomly assigned in an equal allocation ratio (1:1) to either SANTYL or to the hydrogel control according to a pre-determined randomization schedule using a blocking technique. Subject randomization will be stratified by the Subject's wound size at baseline resulting in two possible strata: ≥1.0 and ≤10.0 cm²; and >10.0 and ≤64.0 cm². A blocked design will be used for each individual stratum. In either case, caregivers will apply test article once daily (more often as needed for compromised dressing integrity) for up to 6 weeks.

If the ulcer is closed and completely re-epithelialized prior to the end of the 6 week treatment period in either group, the subject will complete Study Visit 7 (Exit) and will be dismissed from the study.

At each weekly visit, the target ulcer will be photographed and area measured using the ImageIQ EDCIQ mobile imaging system. At Study Visit 1 and at Study Visit 7, the ulcer will be assessed using the PUSH and WBS tools. In addition, resource utilization information will be collected at each study visit as described in Section 9.5.

Figure 8.1-1: Study Flow Chart

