10.2 HANDLING OF MISSING AND INCOMPLETE DATA

The methods used to handle missing or incomplete data for the efficacy and safety measures will be detailed in the Statistical Analysis Plan. For purposes of the primary endpoint, in cases where a photograph is not taken, the Last Observation Carried Forward (LOCF) method will be used. Sensitivity analyses will be conducted as detailed in the following sections to examine the impact of these derivations on the conclusions relating to the primary endpoint.

For purposes of assessments of wound area (and subsequent reductions over the study period), in cases where Study Visit 7 is not attended by the subject, or the area value at the assessment is not recorded or known, the Last Observation Carried Forward (LOCF) method (excluding Study Visit I) will be used.

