Further details, including model assumptions and diagnostics to be examined are included in the study SAP. The preceding analysis will be repeated using the Per Protocol Population.

Kaplan-Meier plots will be presented by treatment, baseline wound area strata, baseline percentage of nonviable tissue and ulcer duration (categorized) and also to represent all covariates with significant effects in the final survival analysis model. Individual plots for multiple factors will be generated where appropriate.

In addition, a sensitivity analysis will be performed to ensure that the efficacy findings are not reliant on assumptions made in either the analysis or derivations. For purposes of the sensitivity analysis, the time to confirmed complete debridement for those subjects discontinuing the treatment period prematurely will be censored at the maximum possible duration of treatment under the study protocol (42 days), rather than time of actual discontinuation. Lastly, the two sensitivity analyses defined in the proportion of subjects achieving complete debridement analysis will be repeated for the time to achieve complete debridement; in these cases the

censoring flag may be modified as detailed previously in the primary analysis, but the time in days will remain unchanged.

The percentage reduction in wound area over the 6-week treatment period and at each assessment visit

Wound area is defined as surface area as measured by the ImageIQ EDCIQ mobile imaging system at each assessment visit by two independent image reviewers. The percentage change in wound area over the 6-week treatment period is then defined as:

Percentage reduction in wound area over 6-week treatment period= $\left(\frac{Area_{SV1} - Area_{SV1}}{Area_{SV1}}\right) \times 100\right)$

In cases where the wound is closed in the opinion of the Investigator, the wound area will be imputed as 0 cm², resulting in a percentage reduction in wound area of 100%. In circumstances where the wound area is missing at the Study Visit 7 for subjects that have not withdrawn prematurely due to closure, the last observation carried forward (LOCF) method will be used.

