An initial linear regression model will contain covariates for treatment, baseline (defined as Study Visit 1) ulcer area, baseline percentage of nonviable tissue, and duration of ulcer. A forward selection procedure will be used for the addition of other baseline covariates with an F-value to attain a significance level of 0.1. Further baseline covariates to be assessed as part of this procedure include: subject age, baseline (maximum) ulcer depth, baseline PUSH and WBS scores. The resulting primary analysis presented will correspond to the final model from the forward selection procedure. The results for the initial model will also be presented. For each of the effects in the initial and final model, the p-value, parameter estimate and corresponding 95% confidence interval will be presented. Secondary subgroup analyses may be conducted as a result of the covariate analyses. Additionally, treatment will be fitted on its own in a further linear regression model. The potential for interactions will be examined by fitting the required interaction terms in addition to those effects in the final linear regression model from the forward selection procedure. In each case if the residuals are not normally distributed then non-parametric bootstrapping will be applied. If the nonparametric bootstrap estimates of the confidence intervals for the difference in mean percentage reduction in area between treatments

differ considerably to the standard model estimates, then the nonparametric bootstrap estimates will be used.

The percentage reduction in wound area over the 6-week treatment period will be summarized by treatment separately by the covariates used in the final model.

In addition, a two-sample t-test will be used to test for a difference between treatments in the mean percentage reduction in wound area between Visit 1 and Visit 2. The test will be repeated for comparisons between Visit 1 and Visits 3, 4, 5 and 6 individually. In each case, if normality assumptions do not hold, a Wilcoxon Rank Sum test will be used.

The wound area, reduction in wound area and percentage reduction in wound area at each study visit will be summarized by treatment separately by baseline wound area strata and overall.

The reduction in percentage non-viable necrotic tissue over the 6-week treatment period and at each assessment visit

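### The plan does not say how ulcers that close before Week 6 enter the Visit 2-6 comparisons; for wound area they drop out by default, and for tissue they may be understated

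*Combined protocol and SAP*

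**What the plan says.** **Early closure.** Protocol section 8.1 states that if the ulcer closes before the end of the 6 weeks, "the subject will complete Study Visit 7 (Exit) and will be dismissed from the study". Section 9.1.3 applies this at the weekly visits: the subject does not complete the visit at which closure is found but should "instead go directly to Study Visit 7 (Exit Visit), be discontinued from treatment and have exit procedures performed". At the exit visit (section 9.1.4) a closed ulcer is photographed and labelled as closed. No percentage of non-viable tissue is attached to that label.

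**By-visit tests.** Section 5 lists the reductions in wound area and in non-viable tissue at each assessment visit among the secondary objectives. For area, section 10.3.2 gives a two-sample t-test from Visit 1 to Visit 2, and then: "The test will be repeated for comparisons between Visit 1 and Visits 3, 4, 5 and 6 individually". A Wilcoxon test replaces it if normality fails. The same tests are repeated for non-viable tissue.

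**Rules for absent values.**
- Area, section 10.2: last observation carried forward applies "in cases where Study Visit 7 is not attended by the subject, or the area value at the assessment is not recorded or known".
- Area, section 10.3.2, carry-forward: it applies "where the wound area is missing at the Study Visit 7 for subjects that have not withdrawn prematurely due to closure".
- Area, section 10.3.2, closed wounds, directly after the formula for the 6-week reduction: "In cases where the wound is closed in the opinion of the Investigator, the wound area will be imputed as 0 cm²".
- Non-viable tissue, section 10.3.2: the last observation is carried forward whenever there is no photograph, with no restriction to Study Visit 7.

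Section 10.2 leaves further missing-data detail to a separate SAP, whose text is not among the supplied pages.

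**The concern.** A subject whose ulcer closes at, say, Visit 4 has no record under Visits 4, 5 or 6. The only later record is the one filed as Study Visit 7. The weekly cells are empty because the ulcer reached the best possible outcome, so the missingness depends directly on what is being compared.

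For area, a program that takes the available data by nominal visit compares only ulcers still open. For tissue, the subject may stay in but with the last reading before closure, which would score a healed ulcer as partly necrotic. With 16 randomized per arm, one or two such subjects can move a weekly mean visibly. These comparisons are a stated secondary objective, so the rule should be fixed before the data are seen.

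**Working it through.** **Step 1. Does any stated rule fill the empty weekly cells?** Take a subject found closed at Visit 4.

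| Rule | Trigger | Fills Visits 4-6? |
|---|---|---|
| Area carry-forward, 10.2 | Study Visit 7 not attended, or its area unknown | No. This subject has a Study Visit 7 |
| Area carry-forward, 10.3.2 | Area missing at Study Visit 7, closure exits excluded | No |
| Closed wound = 0 cm², 10.3.2 | Investigator judges the wound closed | Not stated. It sits under the 6-week measure |
| Tissue carry-forward, 10.3.2 | No photograph taken | Possibly, but with which value? |

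On the last row, the closing photograph is filed under Study Visit 7, which follows Visit 6 in nominal order, and it carries a label rather than a percentage. Carry-forward at Visit 4 would then take the Visit 3 reading. If the early exit were mapped to its actual week and closed were scored 0%, the value would be 0%. The text supports neither step explicitly.

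**Step 2. How much could omission matter for area?** The plan gives no closure rate and no figure for the weekly tests; its sample-size calculation concerns the primary endpoint only. Everything below except the randomized number, the 15% drop-out rate and the two-sided 5% level is therefore assumed.

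Inputs: 14 per arm (16 × 0.85 = 13.6, rounded up); mean reduction among open ulcers 40% on SANTYL and 25% on hydrogel; SD 25.

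With k closures among n subjects and open-ulcer mean m, the arm mean with closures entered is (100k + (n − k)m)/n. With closures omitted it is m.

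- SANTYL, 2 closed: (200 + 12 × 40)/14 = 48.6.
- Hydrogel, 0 closed: 25.0. Difference 48.57 − 25.00 = 23.6, against 40 − 25 = 15 omitted.
- Hydrogel, 1 closed: (100 + 13 × 25)/14 = 30.4. Difference 48.57 − 30.36 = 18.2.
- Hydrogel, 2 closed: (200 + 12 × 25)/14 = 35.7. Difference 48.57 − 35.71 = 12.9.
- One closed in each arm: (100 + 13 × 40)/14 = 44.3 and 30.4. Difference 13.9.

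Power of the two-sample t-test, by simulation:

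| Closures, SANTYL vs hydrogel | Difference: omitted / entered | Power: omitted / entered |
|---|---|---|
| 1 vs 0 | 15 / 19.3 | about 33% / 44% |
| 2 vs 0 | 15 / 23.6 | 31% / 56% |
| 3 vs 0 | 15 / 27.9 | about 30% / 69% |
| 1 vs 1 | 15 / 13.9 | 31% / 16% |
| 2 vs 1 | 15 / 18.2 | 30% / 25% |
| 2 vs 2 | 15 / 12.9 | 29% / 7% |

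In the 2 vs 1 row the difference rises but power falls, because values at 100% also widen the spread within each arm.

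**Step 3. Other assumptions.** With 16 per arm and open-ulcer means of 50% and 30%, omission leaves 20 points.
- 2 vs 0 closures: 26.3 points when entered. Power, omitted against entered, is 56% against 77% at SD 25, and 32% against 52% at SD 35.
- 2 vs 2 closures: 17.5 points when entered. Power is 53% against 27% at SD 25, and 31% against 18% at SD 35.

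The pattern is the same. With no closures the two analyses coincide.

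**The case against.** **The plan never says closed ulcers are dropped.** That is so. The 0 cm² sentence is worded generally, and a careful programmer might apply it to every visit. Omission is what follows from an available-data analysis by nominal visit, not an instruction. This limits the point to a missing rule, but the gap remains: the sentence is not extended to Visits 2-6, and both area carry-forward rules stop at Study Visit 7.

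**Tissue has its own rule.** This also stands. A reader might infer that the tissue tests lose their best responders just as the area tests do. The documents do not support that, because the tissue carry-forward rule is not confined to Study Visit 7. What remains is the value carried: no percentage for a closed ulcer and no mapping of the early exit.

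**The direction of bias is not fixed.** A reader might infer that omission always works against the arm that heals faster. The table shows otherwise: equal closures make omission overstate the difference, and at 2 vs 1 omission understates the difference yet gives higher power.

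**Early closure may be rare.** Entry requires at least 85% necrotic tissue, so full closure in the first weeks may be uncommon. That is an inference; the documents give no rate either way.

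**The SAP may settle it.** It may. But sections 10.2 and 10.3.2 already specify closure and carry-forward handling, and nothing in the supplied text covers these cells.

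**Conclusion.** The point holds as a gap in the by-visit analyses, clearest for wound area. Run by nominal visit on available data, the Visit 2-6 area tests would compare only ulcers still open. The tissue tests may retain closed ulcers but could understate their result.

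The size is unknown. In the assumed 14-per-arm setting, two closures on SANTYL alone move the difference from 15 to 23.6 points when they are entered as 100%; two in each arm move it from 15 to 12.9. The distortion can therefore go either way, depending on how closures split between arms, and is nil if none occur early. These figures rest on assumed means, SD and closure counts, and illustrate the mechanism only.

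The primary endpoint is not affected, and the 6-week area analysis is protected by the 0 cm² rule. This is a cheap improvement to a secondary analysis, not a threat to the main conclusion.

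**What to change.** In sections 10.2 and 10.3.2, state three things:

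1. From the scheduled visit at which closure is found, and at every later scheduled visit through Visit 7, wound area is 0 cm² (100% reduction) and non-viable tissue is 0%.
2. The early exit visit is mapped to its actual study week for analysis.
3. These values enter all by-visit tests and summaries.

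The cost is a short addition to the text and one derivation step; no new data are needed. The rule assumes that a closed ulcer stays closed, which the plan already assumes for the 6-week area value. Values stacked at 100% may trigger the Wilcoxon test that section 10.3.2 already provides.

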9.1.5 Unscheduled Visits

Unscheduled exams may be conducted at the discretion of the Investigator with all obtained information recorded in the source documents and on the Unscheduled Visit pages within the Case Report Form (CRF).

9.1.6 Concomitant Medications

A concomitant medication is any drug or substance administered from Day 1 (SCR 1) of the study through the last study visit. No therapies other than the assigned test article are to be used to treat the target ulcer during the study period. These include:

- Oral steroid use > 5 mg daily
- · Growth factors

- Living skin equivalents (e.g. Apligraf[®], Dermagraft[®])
- Extracellular matrix products (e.g. OASIS®)
- Amniotic membrane products
- Any target ulcer treatment, excluding study treatment, specifically intended to close the wound (topical antibioties are acceptable if needed but study treatment should be withheld and doses would be considered as missed).

The use of concomitant medications used to treat the ulcer and any medications used for the treatment of adverse events must be recorded. Adverse events related to administration of these therapies must be documented appropriately.

9.2 DISCONTINUED SUBJECTS

Discontinued subjects are those who voluntarily discontinue participation, who are withdrawn for safety reasons or use of prohibited concomitant treatments. In all cases the Exit Visit (Study Visit 7) must be completed.

All subjects who discontinue the study prior to completing the regularly-scheduled visits should complete the exit visit procedures described in Section 9.1.4. If appropriate, the Investigator also should advise the subject of subsequent therapy and/or procedures necessary for their medical condition.

9.3 SUBJECT PREGNANCY

Women of child-bearing potential are not excluded from the study provided they are not pregnant at screening as documented by a negative urine pregnancy test. However, if a woman becomes pregnant during the study, Smith & Nephew should be contacted immediately and a decision will be made regarding the continuation in the study of the pregnant woman. Pregnancy is not reportable as an adverse event; however, complications related to the pregnancy may be reportable as determined on a case-by-case basis. Pregnancy-related information will be collected until termination of the pregnancy.

9.4 STUDY METHODS AND MEASUREMENTS

9,4.1 Wound photography and measurement

All wound photographs and measurements will be taken with the ImageIQ EDCIQ mobile imaging system. The system utilizes a portable device (e.g., iPad) that easily allows capture of wound images. Once captured the images are sent to a central database for storage and review. Quantitative measurements and other wound assessment data will be inputted into the EDCIQ system by the independent reviewers. ImageIQ builds that information into an electronic record for review and archiving. Information about the wound's measurement history is available on this system so that the serial progression of wound status can be calculated and presented.

9.4.2 Percentage of Necrotic Tissue and "Complete Debridement"

All wound photographs will be reviewed in a blinded fashion, identified only by subject number, initials, and date of assessment by two independent reviewers. The reviewers will complete an assessment form providing the percentage of the ulcer covered by non-viable, neerotic tissue as measured using the ImageIQ EDCIQ mobile imaging system. In any case where one reviewer selects 0% or "complete debridement", and the second reviewer does not, the photograph will be re-reviewed at a consensus meeting.

9.4.3 Wound Assessment Scales

The PUSH Tool (Version 3.0), specifically developed for pressure ulcers, and the WBS will be used to assess all ulcers at baseline (Study Visit 1), and at Exit. Copies of these instruments are included in the appendices.

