8.2 METHODS USED TO MINIMIZE BIAS

Due to obvious differences in the physical appearance of the test articles, double-blinding of the study medication is not possible. However, assessments of the ulcer debridement status relating to the presence of non-viable necrotic tissue (primary objective) will be carried out in a blinded fashion by two independent assessors using digital photographs identified only by the subject number and date. Blinded assessment is intended to limit the occurrence of conscious and unconscious bias in the assessment and interpretation of the endpoints. In addition, randomization will be sequential according to a pre-determined, computer-generated randomization schedule. In this way the Investigator will not be able to direct a particular subject to a particular treatment thus preventing treatment allocation bias. Ulcer measurements will be carried out using the ImageIQ EDCIQ mobile imaging system which will minimize subjectivity in theses assessments.

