This visit should occur no more than 7 days after the Screening Visit. Any subject who returns but does not qualify at this visit will be a screen failure and will not be randomized. Upon completion of all screening procedures and confirmation that the subject is eligible for the study, the Investigator or designee will randomize the subject using an electronic randomization system (www.sealedenvelope.com) to obtain the treatment assignment.

The day of the week (Monday, Tuesday, etc.) on which this visit occurs will set the weekly visit day for all subsequent assessments/visits (Study Visits 2 through 7) if the subject is randomized. A (± 1) day visit window will be allowed. If an assessment is not made on the original day of the week for Study Visits 2-7, subsequent visits should be scheduled on the original week day. To minimize differences in baseline ulcer size between the two groups, randomized subjects will be stratified by ulcer size determined at this visit [≥ 1.0 and ≤ 10.0 cm²; ≥ 10.0 and ≤ 64.0 cm²]. Once randomized, subjects will be assessed weekly for the duration of the treatment period (SV1 through SV7).

The following procedures will be completed:

- 1. Record any changes in general health and the use of concomitant medications.
- 2. If any adverse events are observed or reported, they must be recorded as instructed in Section 12, *Adverse Events*.
- Review laboratory results from the blood sample and all other inclusion/exclusion
 criteria.
 - If the blood test results qualify and all entry criteria are met, the subject may be randomized.
- Irrigate the wound with normal saline delivered at 4-15 psi using the Irrimax® device.
 (Sharp debridement is NOT allowed.)
- 5. Photograph the target ulcer using the ImageIQ EDCIQ mobile imaging system. The target ulcer area (cm²) and percentage of the target ulcer surface covered with necrotic, nonviable tissue will be determined by two independent reviewers using the ImageIQ EDCIQ mobile imaging system. The target ulcer area and percentage of necrotic, nonviable tissue must be assessed by at least one independent reviewer prior to the subject being randomized.

Note: If the area of the target ulcer is >64.0 cm², the subject must be screen failed and should not be randomized.

- 6. Assess the wound status using both the PUSH and WBS tools.

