18. APPENDICES

18.1 INSTRUMENTS AND SPECIAL INSTRUCTIONS

18.1.1 PUSH Tool version 3.0

The Pressure Ulcer Scale for Healing (PUSH) Tool (12) is a validated instrument that comprises three subscale scores used to assess PU healing: 1) ulcer size (scored on a scale of 0 to 10 points), 2) exudate (scored on a scale of 0 to 3 points), and 3) type of the tissue (scored on a scale of 0 to 4 points). The three subscale scores are added to generate a cumulative wound status score. A cumulative score of 17 indicates poorest PU status and a score of 0 indicates the best possible status.

Figure 18.1-1: PUSH Tool Version 3.0

		L
Ψ,		7
NAT	ION	AL
PIKE	55U	RE
1,11	CEI	
ATTS	150	RY

Pressure Ulcer Scale for Healing (PUSH) PUSH Tool 3.0

Patient Name	Patient ID#
Ulcer Location	Date

Directions:

Observe and measure the pressure ulcer. Categorize the ulcer with respect to surface area, excutate, and type of wound issue, Record a sub-score for each of these ulcer characteristics. Add the sub-scores to obtain the total score. A comparison of total scores measured over time provides an indication of the improvement or deterioration in pressure ulcer heading.

LENGTH	0	1.	2	3	4	5	Sub-score
WIDTH	0	< 0.3	0.2 - 0.6	0.7 - 1.0	1.1 - 2.0	2.1-3.0	
(in cm²)		3.1-4.0	7 4.1 - 8.0	8 8.1 - 12.0	9	10 >240	
EXUDATE AMOUNT	O None	1 Light	2 Moderate	3 Heavy	12.1 - 24.0	324.0	Sub-score
TYPE	Closed	f Epithelial Tissue	2 Granulation Tissue	3 Slough	4 Necrotic Tissue		Sub-score
		•					TOTAL SCORE

Leneth x Wridth: Measure the greatest length (head to toe) and the greatest width (side to side) using a contimeter ruler. Multiply these two measurements (length x width) to obtain an estimate of surface area in square contimeters (cm²). Caveat: Do not guess! Always use a centimeter ruler and always use the same method each time the ulcer's measured.

Exudate Amount: Estimate the amount of exudate (drainage) present after removal of the dressing and before applying any topical agent to the ulcer. Estimate the exudate (drainage) as none, light, moderate, or heavy.

Tissue Type: This refers to the types of fissue that are present in the wound (ulcur) bed. Score as a "4" if there is any necrode tissue present. Score as a "2" if there is any amount of slough present and necrote fissue is absent. Score as a "2" if the wound is clean and contains granulation tissue. A superficial wound that is reepithelializing is scored as a "1". When the wound is closed, score as a "0".

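### PUSH and WBS have no named scorer and no blinding provision, and the Study Visit 1 sequence allows their baseline values to be recorded after allocation is known.

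*Combined protocol and SAP*

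**What the plan says.** **Scope of blinding.** Section 8.2 accepts that "double-blinding of the study medication is not possible" because the two articles differ visibly. It then provides that "assessments of the ulcer debridement status relating to the presence of non-viable necrotic tissue (primary objective) will be carried out in a blinded fashion". The readers are a pair of assessors who see only the images. Section 9.4.2 has those readers report the percentage of non-viable tissue. Section 10.3.2 has image reviewers measure wound area as well. PUSH and WBS appear in none of these provisions.

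**Where the scales are scored.** Section 9.4.3 says they are "used to assess all ulcers at baseline (Study Visit 1), and at Exit". Step 6 of Study Visit 1 (Section 9.1.2) and step 6 of the Exit Visit (Section 9.1.4) carry the same instruction: "Assess the wound status using both the PUSH and WBS tools". No section says who scores.

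**Order at Study Visit 1.** In Section 9.1.2, "the Investigator or designee will randomize the subject using an electronic randomization system". Step 3 permits randomization on one condition: "If the blood test results qualify and all entry criteria are met". Step 5 adds that at least one reader must first have assessed the photograph. Scoring is step 6 and application of the article is step 7. Section 9.1.3 states that "All study procedures should occur in the order outlined in the protocol".

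**Use in the analysis.** Section 10.3.2 compares the reduction in total PUSH, and in total WBS, between arms by Wilcoxon rank-sum test. Section 10.3.1 lists baseline PUSH and WBS among the forward-selection candidates for the primary logistic model.

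**The concern.** Section 8.2 gives the purpose of blinded assessment as limiting bias in how the endpoints are assessed and interpreted, yet two endpoints tested between arms lie outside it. Both scales contain judged items, such as exudate, tissue type, edema and wound edges. If the scorer knows the arm, expectation alone can produce a difference in the reduction.

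The baseline order matters separately. A baseline value should not be open to influence from the allocation. Here it enters the PUSH and WBS endpoints directly, and it may also be selected into the primary model as an adjustment term.

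**Working it through.** **1. Who can know the arm, and when.**

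- *Exit.* Scoring is a site-visit step after up to six weeks of open treatment. The PUSH instructions (Section 18.1.1) call for a ruler and for an exudate estimate when the dressing is removed, which places scoring at the bedside. No blinded site assessor is described. That the scorer knows the arm is therefore a strong inference, not a statement in the text.
- *Study Visit 1.* The earliest point at which randomization is allowed is after the reader's check of the step 5 photograph. Two sequences comply: photograph, randomize, score, apply; or photograph, score, randomize, apply. Nothing requires the second.

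**2. How a shift enters the endpoint.** The plan defines reduction = Visit 1 score − Exit score. If scorers rate one arm b₀ points higher at baseline and b₁ points lower at exit, relative to the other arm, the apparent between-arm difference is b₀ + b₁ with no true effect. A 1-point total could come from exit alone or be split between the two visits.

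**3. How much of PUSH a photograph can carry.** Section 18.1.1 gives size 0–10, exudate 0–3 and tissue type 0–4.

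- Total: 10 + 3 + 4 = 17, which reproduces the stated maximum.
- Size plus tissue type: 10 + 4 = 14, and 14/17 = 82%.
- Tissue type alone: 4/17 = 24%.
- Exudate alone: 3/17 = 18%.

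Which figure applies depends on two passages that conflict. Section 9.4.1 says all wound measurements use the imaging system; Section 18.1.1 says a ruler is always used, for length × width. The readers supply surface area, which is not length × width. So 14 of 17 holds only if an image-based size band is accepted; if the ruler is mandatory, it is 4 of 17.

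WBS has eight items scored 0–2 (8 × 2 = 16). All eight are scored at the site.

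**4. Illustration of size.** The documents give no SD for PUSH change and no rater shift, so both are assumed. I simulated the planned two-sided Wilcoxon test at 5% on normal data with no true effect, 100,000 runs per cell. Arm sizes were 13 (26 evaluable, Section 11) and 16 (32 randomized).

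| Assumed shift | Assumed SD | 13 per arm | 16 per arm |
|---|---|---|---|
| 0 | any | about 4% | about 5% |
| 0.5 point | 2 | 8.2% | 9.7% |
| 0.5 point | 3 | 6.0% | 6.9% |
| 0.5 point | 4 | 5.4% | 6.0% |
| 1 point | 2 | 20.6% | 25.7% |
| 1 point | 3 | 11.5% | 13.9% |
| 1 point | 4 | 8.4% | 9.6% |

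The effect is clear if the shift is a full point and the SD is small, and slight if the shift is half a point and the SD is 3 or more.

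**The case against.** Several counter-arguments have weight.

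- **Blinded checks exist.** Wound area and percentage of non-viable tissue are compared between arms from image readings, and PUSH sub-scores are summarized by treatment. A bedside PUSH gain with no counterpart in those results would stand out. A reader might infer that nothing planned could expose biased scoring; that goes too far. What remains is that exudate and most WBS items have no blinded counterpart, and that no PUSH or WBS sensitivity analysis is planned, unlike for the debridement endpoints.
- **Baseline room for bias is limited.** Entry requires at least 85% necrotic tissue, so baseline tissue type is near its ceiling, and PUSH size is a ruler measurement in fixed bands. This stands for PUSH size and tissue type, less so for exudate and WBS.
- **The text is compatible with scoring before allocation.** True. A reader might infer that baseline scoring is done unblinded; the protocol supports only that it may be.
- **An image-based PUSH score is not PUSH.** Also true. It departs from the ruler rule, and Section 4.2 commits to the same measurement tools as the earlier trial. It can stand only as a supportive result beside the bedside total.

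**Conclusion.** The point holds as a minor, inexpensive improvement. The documents establish that PUSH and WBS have no named scorer and no blinding, and that baseline scoring is not required to precede allocation. That the exit scorer knows the arm is a strong inference; that the baseline scorer does is only a possibility.

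The false-positive figures, about 5% to 26% across the cases with a shift, show what assumed shifts would do. They are not estimates for this trial.

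Two stronger readings are not supported. The primary endpoint is not compromised: its status comes from blinded photograph readings. The only route to the primary analysis is through baseline PUSH or WBS as selected covariates, and nothing in the documents allows that effect to be sized. Nor would photograph scoring close most of the gap: even with image size accepted, PUSH exudate and all eight WBS items remain unblinded at exit.

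**What to change.** 1. **Section 9.1.2:** require baseline PUSH and WBS to be completed and recorded before the randomization call. This fixes the order of one step and costs nothing.
2. **Section 9.4.3:** state who scores PUSH and WBS at each visit and whether that person knows the arm. One sentence.
3. **Sections 9.4.1 and 18.1.1:** reconcile the imaging-system and ruler statements for PUSH size.
4. **Optional, supportive:** have the two existing blinded readers record PUSH tissue type (0–4) from the Visit 1 and exit photographs, and combine it with a size band taken from their imaging-system area. Report this as a modified image-based score beside the bedside total. The cost is one form field at two visits (32 × 2 = 64 subject-visits per reader), one table and a disagreement rule, since the consensus rule in Section 9.4.2 covers only complete debridement.
5. **Reporting:** interpret the PUSH and WBS comparisons against the blinded area and percentage non-viable tissue results, and say that exudate and all WBS items were scored without blinding. No change to sample size.
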